Gait velocity will be measured using a 4.88 m long instrumented carpet (GAITRite, CIR Systems Inc., Clifton, NJ). The carpet is composed of 18,432 force sensing sensors arranged in a 48 wide x 384 long grid. Data are sampled at either 60, 120, or 240 Hz. The GAITRite is interfaced with a laptop computer that runs software to calculate variables related to gait performance. The GAITRite system is a valid instrument for determining gait velocity and other spatiotemporal parameters. In the testing procedures, participants walk across the carpet, beginning 2 m in front of the carpet and walking 2 m past the end of the carpet to allow for acceleration and deceleration. Participants make multiple passes over the carpet at either the preferred (4 trials) or fast (4 trials) velocity. At the preferred velocity, participants are told to walk “at a pace that feels comfortable to you (as if you were walking to the mailbox or window shopping at the mall).” At the fast velocity the instructions are to walk “as quickly as you can without running.” The software calculates individual trial and average data on gait velocity and spatiotemporal gait characteristics and these data can be exported for further analysis. Summary data on velocity (m/sec; averaged over the 4 usual and 4 fast trials) and the average of the left and right leg for double support (percent of cycle), single support (percent of cycle), stance (percent of cycle), swing (percent of cycle), stride length (cm), and base width (cm) for both the usual and fast trials will be used in analysis.

Falls will be defined as an event whereby an individual unexpectedly comes to rest on the ground or another lower level. Participants will be provided monthly fall calendars, considered the “gold standard”,³⁸ and asked to mark any falls that occur on the calendar. Completion of monthly fall calendars will be monitored via monthly phone calls and collected at the 4- and 12-month visits. Total number of falls over the 12-month follow-up will be used in analysis.

Single fiber-type composition and fiber size will be examined in muscle biopsies using the ATPase, pH 9.4 and 4.6 technique, combined with laminin immunostaining in 10 μ m muscle sections and the absolute and relative number of type I, IIA, IIX fiber subtypes and their cross-sectional area quantified. The relative number of fiber type and their cross-sectional area at baseline and 4-month follow-up will be used in analysis.

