Single type I and type II muscle fiber contraction force, shortening velocity, and power will be examined in 10-15 fibers per muscle biopsy sample. For single muscle fiber preparation, physiologic tests, and experimental procedures, we will follow described techniques.^{39,40} Briefly, a slack test will be used to determine the unloaded shortening velocity (V_o). The force/velocity relationship will be determined by performing a series of isotonic contractions of the muscle fiber.⁴¹ The muscle fiber will be placed in activating solution (pCa 4.5) and, after it reaches peak force, subjected to three isotonic steps varying from 3-80% of P_o . After the final step, the fiber is rapidly (<1ms) slackened by 20% of its length. This zeroes the force transducer, providing a baseline for force measurement. Shortening velocity and force will be assessed over the final half of each step, and force averaged over the last half of each step. Velocity will be calculated as the slope of the position recorded over the same time period. A total of 5-6 isotonic contraction series will be performed, generating 15-18 pairs of velocity and relative force measurements. Data will be fit to the Hill equation using an iterative, nonlinear curve-fitting procedure to draw the force/power relationship. All forces will be normalized to the fiber's cross sectional area. At the end of each functional experiment, the single-fiber segment will be used to determine myosin heavy chain (MHC) composition using silver staining.^{41,42} Fibers will be excluded from analysis if force declines more than 10% or if fibers break or show partial myofibrillar tearing during the experimental protocol. Absolute fiber force (slk max mN), normalized fiber force to cross-sectional area (slk pk kN/m²), unloaded shortening velocity (V_o , FL/s), the velocity extrapolated to a force of zero (FV V_{max} , FL/s), power (uN*FL/s), and normalized power (W/liter) by fiber type (I or II) at baseline and 4-month follow-up will be used in analysis.

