Type I and type II denervated myofibers will be identified using ATPase pH 9 plus NCAM immunostaining analysis. The whole muscle biopsy will be cryosectioned and 10-12 slices will be mounted per slide. Alternate slides will be stained for NCAM and positive fibers and their expression pattern (perimeter or whole cross section) will be reported as a percent of the total number of fibers. Additionally, fiber grouping (the area occupied by at least two contiguous fibers expressing a predominantly similar myosin heavy chain isoform – type I or II, fully surrounded by fibers of the same predominant myosin heavy chain), a classical evidence of a neurogenic process, will be examined. NCAM+ number and density (NCAM+ number per cross sectional area) and fiber grouping (%) by fiber type (I or II) at baseline and 4-month follow-up will be used in analysis.

Regulation of Runx1 and its dependent genes will be assessed by RNA extraction using the TRIzol method (Invitrogen). Runx1 and its dependent genes will be measured by qRT-PCR and normalized to GAPDH expression. We will use the cycle threshold (CT), defined as the number of cycles required for the fluorescent signal to cross the threshold, as the parameter to calculate $2^{-\Delta\Delta CT}$, which is needed to compare the gene expression in two different samples. Expression of Runx1, Chrny, Scn5a, Myh3, Myog, NCAM1 at baseline and 4-month follow-up will be used in analysis.

Satellite cell differentiation will be assessed in serial muscle cross sections immunostained for Pax7/NCAM satellite cells (SCs). SC number and density (SC per cross sectional area) by fiber type (I or II) at baseline and 4-month follow-up will be used in analysis.

Vitamin D Receptor (VDR) expression will be measured by Western blots using the C20 antibody raised against a peptide mapping at the C terminus of VDR and normalized to actin used as a loading control. VDR concentration at baseline and 4-month follow-up will be used in analysis.

Exploratory outcomes (Wake Forest Pepper Center Pilot; [name], PI)

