For the muscle biopsy subsample (n=16 per group), primary analyses will proceed on the “intent-to-treat” principle in which data from all randomized participants are used in analyses. All participants who complete the 4-month muscle biopsy and on whom the muscle fiber testing can be completed will be included in the analytic sample. Even if participants wish to discontinue the supplements, we will still attempt to follow them for outcomes in order to do the intention-to-treat analysis at 4 months. Characteristics of the participants missing the 4-month follow-up outcomes will be compared to participants without missing data using chi-square tests and t-tests to determine if there are any differences with regard to intervention group, demographic characteristics, baseline physical performance, and baseline muscle fiber testing. Our primary statistical analyses will focus on testing the primary hypotheses that, compared to placebo, vitamin D supplementation will result in changes in skeletal muscle composition and physiology as quantified by: fiber-type composition and size; fiber force, shortening velocity, and power; NCAM+ myofibers; Runx1, Chrn γ , Scn5a, Myh3, Myog, and NCAM1 expression; SC number; VDR expression; and bioenergetic capacity. For our primary outcome of percent type II fibers we will use analysis of covariance (ANCOVA) to model differences in percent of type II fibers between the two groups, with adjustment for the baseline measure, age, gender, and race. Analysis of other continuous measures will also use the ANCOVA model to compare the groups adjusted for age, gender, and race. In secondary analyses, we will examine if the percent of participants who have a relative increase in type II fibers of 25% or more from baseline differs by intervention group using Fisher’s Exact Test, and in logistic regression models adjusted for age, gender, and race. Furthermore, we will explore if the relationship between vitamin D supplementation and neuromuscular function is mediated by change in muscle composition and physiology by including the variables described above as covariates in the ANCOVA model described above. If the relationship between vitamin D supplementation and power decreases by 10% or more, it will be considered evidence of partial mediation.

Human Subjects Protection

Subject Recruitment Methods

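### The covariate list for biopsy outcomes other than percent type II fibers does not name the outcome's own baseline value; the plan should state that it is included

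*Combined protocol and SAP*

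**What the plan says.** The paragraph on the muscle biopsy subsample in Statistical Analyses contains two adjacent sentences with different covariate lists. Percent type II fibers is modelled by ANCOVA "with adjustment for the baseline measure, age, gender, and race". Then: "Analysis of other continuous measures will also use the ANCOVA model to compare the groups adjusted for age, gender, and race". The hypotheses in the same paragraph are worded as changes: "vitamin D supplementation will result in changes in skeletal muscle composition and physiology as quantified by", followed by fiber size, single-fiber function, denervation markers, gene expression, satellite cells, vitamin D receptor and other measures.

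Under Outcome measures, baseline and 4-month values are both named for these outcomes. For fiber type and size: "The relative number of fiber type and their cross-sectional area at baseline and 4-month follow-up will be used in analysis". For single-fiber function: "normalized power (W/liter) by fiber type (I or II) at baseline and 4-month follow-up will be used in analysis". For genes: "Expression of Runx1, Chrny, Scn5a, Myh3, Myog, NCAM1 at baseline and 4-month follow-up will be used in analysis". None of these sentences says how the baseline value enters the model, or whether the dependent variable is the 4-month value or the change.

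**The concern.** Where the plan otherwise describes a baseline-adjusted comparison, it names the baseline term: in the leg-power sample size, in the main-trial mixed model, and for percent type II fibers. A restated list without that term can therefore be read as a different model.

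That one sentence governs many variables. Counting those defined under Outcome measures gives 12 single-fiber variables (six measures by two fiber types), 6 for NCAM and fiber grouping, 6 genes, 4 for satellite cells and 1 for the vitamin D receptor. That is 12 + 6 + 6 + 4 + 1 = 29, with fiber size in addition. Several are secondary outcomes under Hypothesis 2. With 16 per group, precision is scarce and the baseline biopsy has already been taken, so a model that ignores it, or uses it only through subtraction, can waste information. The open wording also leaves the baseline term and the outcome scale to be settled after the data are seen.

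**Working it through.** **The plan's own figure.** Statistical Power gives 16 per group for a difference of 25 with SD 23.7, a two-group t-test, two-sided 0.05 and 80% power. The standardised difference is 25/23.7 = 1.055. The normal approximation gives 2 × (1.960 + 0.842)² / 1.055² = 14.1, so 15. The exact noncentral-t power is 0.796 at 15 and 0.823 at 16, so 16 reproduces, and 16/0.9 = 17.8 rounds up to the planned 18. The calculation uses an unadjusted test on the primary biopsy outcome, so nothing below changes it.

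**Inputs for the other outcomes.** n is 16 per group, 32 in all. The baseline to 4-month correlation r is not given for any biopsy outcome, so it is assumed to lie between 0 and 0.7. The 0.43 (Table 3 footnote) and 0.708 (leg power) in Statistical Power refer to functional outcomes and serve only as markers on that range. Two further assumptions are that the SD is equal at both visits and that race takes one degree of freedom.

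**Formulas.** With a common SD σ, the residual variance is:
- σ²(1 − r²) with baseline as covariate;
- 2σ²(1 − r) for a change score without it;
- σ² for the 4-month value alone.

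The large-sample ratio of standard errors, with baseline over without, is therefore √((1 + r)/2) against the change score and √(1 − r²) against the 4-month value alone.

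**Cost of the extra covariate.** Error degrees of freedom fall from 32 − 5 = 27 to 32 − 6 = 26, and the critical t rises from 2.052 to 2.056. Chance imbalance in baseline adds a little more. Simulation with 16 per group and 20,000 runs per r puts the total at a factor of 1.021 when r = 0.

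**Check by hand.** At r = 0.43 against the change score: √(1.43/2) = 0.846, and 0.846 × 1.021 = 0.863. At r = 0.7: √(1.7/2) = 0.922, and 0.922 × 1.021 = 0.941. The simulated ratios are 0.863 and 0.940.

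**Simulated ratios of 95% CI width, with baseline over without:**

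| r (assumed) | against change score | against 4-month value alone |
|---|---|---|
| 0 | 0.722 | 1.021 |
| 0.2 | 0.792 | 0.999 |
| 0.43 | 0.863 | 0.921 |
| 0.5 | 0.884 | 0.884 |
| 0.7 | 0.940 | 0.730 |

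Once baseline is a covariate, the change and the 4-month value give the same treatment estimate and interval, so that choice no longer matters.

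**In power terms.** An effect with 80% power under baseline adjustment would have about 66% power at r = 0.43 and 74% at r = 0.708 if change is analysed without baseline. This calculation charges the lost degree of freedom but not the chance imbalance, so it slightly overstates the loss.

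**Gene expression.** The plan computes 2^(−ΔΔCT), "which is needed to compare the gene expression in two different samples", and does not name the reference sample. If the reference is the participant's own baseline, then ΔΔCT at baseline is 0 and the value is 2⁰ = 1 for everyone. A constant cannot serve as a covariate.

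**The case against.** The strongest reply is that baseline is already in. The sentence says that the other measures also use the ANCOVA model, which points back to the model just described, and that model includes baseline. The plan may use the same shorthand elsewhere: the main-trial mixed model lists baseline, age, gender and race, and the secondary contrasts that follow are said to be adjusted for age, gender, race and season, with no sign that baseline was removed. This stands. It does not prove carry-over, but it makes the short list weak evidence of a deliberate omission. A reader might infer that the plan has chosen an analysis without baseline; the documents do not support that.

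Second, a reader might take the 27% figure at r = 0.7 as the size of the problem. It belongs to a model of the 4-month value alone, which fits poorly with hypotheses stated as changes and with the statements that baseline values will be used. The change-score column is the closer reading, and there the gain at r = 0.7 is 6%. The 28% gain in that column requires a baseline that says nothing about follow-up.

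Third, some assays may have low r, since single-fiber function "will be examined in 10-15 fibers per muscle biopsy sample". Against the 4-month value alone, adding baseline gains nothing below r of about 0.2. Against a change score it gains at every r examined.

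Fourth, the gene-expression point is conditional. The plan speaks of expression at both visits, which suggests a value at each, and nothing says that the reference is the participant's own baseline. It is a caution for the wording of the fix, not a fault found.

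**Conclusion.** The point holds as an ambiguity with a possible loss of precision. It is minor. If baseline carries over, the loss is zero. If the list is followed literally and change is analysed, adding baseline would narrow the 95% interval by about 14% at r = 0.43 and 6% at r = 0.7, and by more at lower r (21% at 0.2). If only the 4-month value were modelled, the effect of adding baseline runs from about 2% wider at r = 0 to 27% narrower at r = 0.7. Every percentage rests on an assumed r, on equal SDs at the two visits and on one degree of freedom for race. The documents cannot settle which reading was intended.

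Two stronger inferences are not supported. The omission would not bias the treatment comparison, because treatment is randomised; it would only leave chance baseline imbalance uncorrected (4-month value) or over-corrected (change score). It also does not weaken the substudy's primary result, because percent type II fibers already has its baseline in the model and the 16 per group reproduces.

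**What to change.** Reword the sentence on other continuous measures so that each continuous biopsy outcome measured at baseline and 4 months is analysed by ANCOVA adjusted for its own baseline value, age, gender and race, as is already written for percent type II fibers. Either the 4-month value or the change may be the dependent variable; name one.

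For gene expression, specify a scale with a separate value at each visit, for example ΔCT, so that the baseline value is not a constant.

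The cost is one clause, a short statement of the gene-expression scale, and one error degree of freedom per model (26 instead of 27). The downside is at most an interval about 2% wider, and only where baseline is uninformative and the alternative was the 4-month value alone. No new data are needed.

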Short Physical Performance Battery score ³⁰	2.05	0.92
Timed Up and Go, sec ⁸²	5.40	2.43
20-m Gait Speed, m/sec ³¹	0.15	0.07
Lower extremity muscle strength, Nm ³¹	21.0	9.5
Postural Sway, mm ¹²²		
Mediolateral (ML) displacement	2.7	1.2
Anteroposterior (AP) displacement	3.9	1.8

*SD calculated assuming a correlation of 0.43 between baseline and follow-up measures.

For the muscle biopsy subsample, we have powered on a difference between the two groups of a relative increase in type II fibers of 25% or more. In our preliminary data in older adults with 25(OH)D concentrations <25 ng/mL treated with 2000 IU/d vitamin D₃ plus 1200 mg/d calcium (n=4) or calcium only (n=2), a 1 ng/mL increase in 25(OH)D concentration was associated with a 2.35% relative increase in type II fibers over 4 months. Assuming that 25(OH)D concentrations will increase by an average of 14 ng/mL in the intervention group, we

expect to see a relative increase in type II fibers of approximately 33%. To allow for the possibility that there may be some increase in the control group due to “drop in” by starting vitamin D supplements or changes in physical activity, a 25% difference between the two groups in the relative increase in type II fibers was selected. Two previously published vitamin D supplementation studies observed increases in type II fibers of 31-34%⁴⁸ and 202%.⁴⁹ Thus, the detectable 25% relative increase is in line with independent observations. A sample size of 16 in each group will have 80% power to detect a difference of 25% assuming that the common standard deviation is 23.7 (based on preliminary data of n=17 participants in a behavioral intervention with data on change in type II muscle fibers) using a two group t-test with a 0.05 two-sided significance level. Allowing for 10% drop out, we will inflate the sample size to 18 per group, for a total of 36 participants. However, up to 40 participants may be approached for a baseline muscle biopsy to allow for biopsy samples that yield insufficient muscle for analyses.

Statistical Analyses

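### The adjusted logistic model for type II fiber responders has about 10 to 14 expected events for at least four terms, so standard maximum likelihood would inflate the odds ratio under a real effect; a Firth penalty should be specified

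*Combined protocol and SAP*

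**What the plan says.** The Statistical Analyses section gives the size of the biopsy analysis as "For the muscle biopsy subsample (n=16 per group"). The primary analysis of percent type II fibers is an ANCOVA adjusted for baseline, age, gender and race. A secondary analysis then counts as responders those whose type II fibers rise, relative to their own baseline, by at least a quarter. The two arms are compared on this outcome in two ways. The first is Fisher's test. The second is described as follows: "and in logistic regression models adjusted for age, gender, and race".

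The Statistical Power section supplies the figures behind the substudy. The sample size statement reads "A sample size of 16 in each group will have 80% power to detect a difference of 25" (a percentage). The variability it rests on is stated as "common standard deviation is 23.7", and the calculation is a two-sided t-test at the 0.05 level. The section expects a rise of about 33% on vitamin D and chose 25 points to leave room for some rise on placebo, which it does not quantify.

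The combined document gives no expected responder rate, no number of race categories, no estimation method for the logistic models, and no fallback if the data are sparse or separate.

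**The concern.** A responder outcome in 32 people yields few events, and the model asks for a treatment term plus at least three covariate terms. At that ratio, maximum likelihood has two known faults. It pushes a real odds ratio away from 1. It also has no finite solution when some combination of the terms predicts the outcome perfectly.

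The plan names no effect estimate or interval to go with Fisher's test, so the adjusted odds ratio is the only model-based measure of the responder effect. If the fit failed, the analyst would have to choose a remedy (drop race, merge categories, change method) after seeing the data.

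**Working it through.** **The plan's own figure.** With difference 25, SD 23.7, two-sided 0.05 and a two-group t-test, exact power is 82.3% at 16 per group and 79.6% at 15. So 16 per group is right for 80%. Allowing for 10% dropout, 16 / 0.9 = 17.8, rounded up to 18 per group and 36 in total. The stated sample size reproduces.

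**Expected responders.** Assume normally distributed relative change with SD 23.7. The chance of responding is then 1 − Φ((25 − mean) / 23.7), multiplied by 16 per arm. The documents do not give the placebo mean, so two values are used: 0, and 8 (33 − 25).

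| Mean change, vitamin D vs placebo | Responder chance | Expected events | True odds ratio | Events per term (4 terms) |
|---|---|---|---|---|
| 25% vs 0% | 50.0% vs 14.6% | 8.0 + 2.3 = 10.3 | 5.86 | 2.6 |
| 33% vs 8% | 63.2% vs 23.7% | 10.1 + 3.8 = 13.9 | 5.54 | 3.5 |
| 0% vs 0% | 14.6% vs 14.6% | 2.3 + 2.3 = 4.7 | 1.00 | 1.2 |

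The four terms are treatment, age, gender and one race indicator. More race categories would add terms.

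**Simulation.** Each scenario used 1,500 to 3,000 trials of 16 per arm, with half women, one binary race indicator with a minority share of 12.5% to 50%, and covariates without effect. None of these settings is in the documents. The model was standard maximum likelihood on the four terms.

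| Result | 25% vs 0% | 33% vs 8% | No effect (0% vs 0%) |
|---|---|---|---|
| Treatment odds ratio not finite | about 8% to 10% | 2% to 3% | 12% to 18% |
| Any coefficient not finite | 10% to 25% | 3% to 13% | about 40% to 45% |
| Median odds ratio when finite | about 7.1 to 7.8 | about 7.2 to 7.6 | about 1.0 |
| True odds ratio | 5.86 | 5.54 | 1.00 |

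The lowest inflation of the median is 7.13 / 5.86 = 1.22 and the highest is 7.59 / 5.54 = 1.37, so it is about 22% to 37% too high. Roughly 58% to 63% of finite estimates lie above the true value.

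The gap between the first two rows is mainly the race coefficient diverging while the treatment estimate stays finite. If a second race indicator covered only two people, some coefficient would diverge in 60% to 63% of trials, but the treatment odds ratio in only about 10%.

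**Firth-penalised logistic regression on the same kind of data.** Estimates were always finite. The mean log odds ratio was 1.78 to 1.83 against a true 1.77 (25% vs 0%), and 1.74 to 1.77 against 1.71 (33% vs 8%). The median odds ratio was about 5.4 to 5.7 against 5.86, and about 5.2 to 5.5 against 5.54, so slightly low.

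**The case against.** The strongest reply is that little rests on this model. It is a secondary analysis with no sample size behind it. Fisher's exact test is named first for the same comparison and is valid at this size. The powered outcome is the continuous fiber percentage by ANCOVA. All of that stands, and it sets the weight of the point.

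A second reply is that the bias is small beside the noise. On the log scale the inflation is ln 1.22 = 0.20 to ln 1.37 = 0.31, while the median standard error of the adjusted estimate in simulation is about 0.97 at 10 events and 0.90 at 14. This also stands: a Firth penalty corrects the centre of the estimate but does not make 32 people informative.

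A third reply is that the plan says only logistic regression and does not commit to maximum likelihood. That is true. Maximum likelihood is taken here as what the unqualified term would normally mean, and a penalised fit would be consistent with the text. The gap is that the plan does not ask for one.

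Two stronger readings are tempting, and the documents support neither:

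- **That the treatment odds ratio will often not exist.** Under the design effect it fails in about 2% to 10% of trials. The higher failure rates count any diverging coefficient, chiefly race, and they are highest when there is no effect or when a race category is very small.
- **That any reported odds ratio will exaggerate the effect.** About 4 in 10 finite estimates fall below the true value, and with no effect the median is about 1.0.

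**Conclusion.** The point holds as a cheap improvement to a secondary analysis. About 10 to 14 expected responders for at least four terms is too few for standard maximum likelihood to give a well-centred odds ratio. Under a real effect of the planned size, the median is roughly 22% to 37% too high. The upward shift appears in both the 10-event and the 14-event scenarios, so it does not depend on assuming no change on placebo.

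The sizes rest on normal changes, a binary race indicator, an even gender split and covariates without effect. In one run with moderate covariate effects (25% vs 0%), 11% of fits were non-finite and the median odds ratio was 8.6. Part of that rise is the conditional odds ratio being larger than the marginal 5.86, so it should not be read as extra bias. The primary ANCOVA, the substudy sample size and Fisher's test are not in question.

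**What to change.** In the biopsy part of the Statistical Analyses section, state that the adjusted responder odds ratio will be estimated by Firth-penalised logistic regression with profile-likelihood intervals. Keep Fisher's exact test, and add an exact confidence interval for the difference in responder proportions.

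Dropping the adjusted model altogether is not recommended. Gender and race are blocking factors in the treatment randomization, and that option would give up adjustment for them.

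The cost is a small change to the SAP wording and slight shrinkage of the estimate, with no change to sample size, data collection or the primary analysis. Imprecision at 32 participants remains, and the result should be reported with that in view.
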